## Study Protocol

The second year of "A Trauma-Informed Approach for Positive Youth Development for Montana Students" will continue in the same format as winter 2020, but with 35 participants in an experimental group, along with 20 students in a control group within the same school and enrolled in classes by the same physical education teacher. District leaders wish to hold the study during the Jan-March 2021 window, as this timeframe has shown a historical spike in inappropriate student behaviors and absenteeism. Twice weekly 45-minute sessions during the 8-week intervention period will occur within two physical education classes in order to draw enough participants to gauge statistical significance with resulting data; a third physical education class with the same teacher will serve as the control group for the study, therefore creating 3 gym class clusters, which will allow for computer-generated randomization. Instead of individuals being randomly assigned, gym class clusters of individuals will be randomly allocated to intervention groups. Control group participants will also be offered 8 weeks of yoga after the study concludes.

Student incentives for at least a 75% attendance record in the experimental group include receiving a Fitbit Inspire HR for the study to track their physical health data and students will retain these to encourage healthy exercise and sleep patterns following the study. Teacher incentives for completion of surveys include classroom supply money (funneled through school administration). Gift cards will be provided to parents/guardians who complete the surveys about their child; these will be disseminated by school officials for parents to pick up at the high school, or they may be mailed by the PI on request. Control group participants will also each receive Fitbit Inspire HR upon completion of all pre- and post-survey measures as an incentive.

Data will be collected in a way to best protect student privacy and confidentiality; all surveys will request that participants self-identify through a confidential code provided by the PI, and all reflective journals will be labeled with this code as well. Cortisol tubes will also be labeled with this unique code. The PI will maintain the code key in an encrypted computer file, which can only be unlocked with an access code that is known only by the PI; this computer will be kept in a locked office at all times, and all data will be securely destroyed (either by computer deletion or secure shredding) no later than one year after the conclusion of the study.

The intervention might bring up strong emotions for the participants; so too might the administration of the ACE survey during preliminary data collection. To mitigate this potential, the PI will caution students that this may occur and emphasize the importance of self-care and knowing one's own limits. Immediate referrals regarding suicidality, self-harm, depressive thoughts, etc. will be directed to the school nurse. If needed, referrals for additional, outside treatment will be provided as determined by school officials and/or requested by the participant and/or the participant's legal guardian(s). Additional resources for outside assistance will be shared with participants; these resources, along with processes for reporting and responding to adverse outcomes, can be found in the study's Human Subjects form and on student assent and parent consent forms.

Participants in this feasibility study may have reductions in severity of depression and/or anxiety as well as improvements in overall behavioral health and well-being. If needed, referrals for additional, outside treatment will be provided, as determined by school officials and/or requested by the participant and/or the participant's legal guardian(s). Benefits also include vital data to inform other potential interventions.

**Aim 1:** Pilot test a trauma-informed yoga intervention for 15-18 year-old male and female high school students.

To prepare for pilot study year 2, feedback has been gathered from the school district, teachers, and students via focus groups and email communications to assess the burden from the various assessment instruments and participation in the pilot. Assessment measures listed below comport with this feedback. Retention and satisfaction of participants, as measured by survey instrumentation from year 1 has indicated the need for an ongoing partnership with the school district and an expansion to additional high school physical education classes (8-week intervention, n=35). During year 2, the study will compare results between the experimental group and a new 20-participant control group, which will be located within the same school setting. The intervention’s effectiveness for youth mental and physical health will be assessed with: surveys measuring depressive and anxiety symptomology; and a wearable fitness tracker (added in year 2) with cortisol testing to measure physiological changes (e.g., resting heart rate and sleep cycle patterns).

**Aim 2:** We will implement a limited feasibility study of partial online yoga delivery via Zoom within the context of the pilot study’s physical education classes to explore scalability to rural communities without access to yoga instructors as well as provide a contingency for COVID-19 school closures.

One session will be held during the PE class period with the yoga instructor teaching remotely to the entire class; another will be held outside of the regular school day with participants attending synchronously from home at a time to be determined by surveying participants’ preferences and availability; both sessions will have a 75% participation rate goal. Qualitative feedback will be gathered from both the yoga instructor and participants on their remote experiences. Remote delivery will also be provided for the control group following the conclusion of the study.

**Aim 3:** Evaluate the study’s school-community-academic partnership at the conclusion of the program using a mixed methods survey. The results will be compared using paired *t* tests with data from the same survey, collected at the end of year 1. The CAB will meet monthly to determine program adjustments. Survey administration and data analysis will occur in summer 2021. The PI will share results with the CAB to determine areas for program refinement and assess need for study continuation with a year 3 expansion.

**Sources of Materials.** Assessment measures will include the following:

Description of Measure	Source (if applicable)	Timeline for Dissemination	Cronbach’s Alpha/Validity & Reliability
Center for Youth Wellness ACE-Q Self-Reporting Screener for Teens	Burke-Harris & Renschler, 2015	Pre-intervention (in order to determine ACE scores of participants)	Longitudinal testing currently underway to measure content and construct validity/reliability
Generalized Anxiety Disorder Scale (GAD-7)	Spitzer et al., 2006	Pre- and post-intervention	Cronbach’s alpha: .79-.91 Reliability = .85

			Validity = 73.3%
Patient Health Questionnaire for Depressive Symptomology for Adolescents (PHQ-A)	Johnson, 2002	Pre- and post-intervention	Chronbach's alpha = .835 Reliability = .875 Validity = 89.5%
Strengths and Difficulties Questionnaire for ages 11-17 (SDQ Self-Report 11-17), Teachers and Parents Report (SDQ-Teacher/Parent Report 11-17)	Goodman, 2005	Pre- and post-intervention	Chronbach's alpha = .86 Reliability and validity vary according to respondent type and age of child self-reporting
Cortisol salivary assays	Salimetrics Laboratories	Pre (beginning of week 1)-, mid- (week 4) and post-intervention (end of week 8)	Mean accuracy of salivary cortisol testing > 90%
Resting heart rate and sleep cycle data (collected from the wearable fitness tracker, Fitbit Inspire HR)	Fitabase Cloud-Based Data Management System	Pre- (1 week prior to intervention to establish a baseline), mid- (week 4) and post-intervention (at conclusion of week 8) (collected through cloud-based data management system, Fitabase)	Heart rate measure = mean margin of error 5.96% and mean agreement of 91% with ECG data Sleep: Cohen's kappa 0.52-0.53 +/- 0.14; per-epoch accuracy of 69%
Collection of secondary data, including attendance and academic data (MAPS benchmark/progress monitoring standardized assessment scores, attendance, and office referrals)	N/A	Office referrals/behavioral data: Collected 8 weeks prior to study and during 8 weeks of intervention for comparison Attendance data: Collected 8 weeks prior to study and during 8 weeks of intervention for comparison MAPS: Pre- and post-intervention	MAPS Data: Pearson correlation coefficients range from .76-.82 in reading and .82-.86 in mathematics  Other measures: N/A

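### The Fitbit is earned by attendance in the experimental arm and by survey completion in the control arm, so an attendance reward cannot be separated from yoga when attendance is compared between arms

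*Combined protocol and SAP*

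**What the plan says.** The incentive paragraph of the Study Protocol gives the experimental-arm rule: "Student incentives for at least a 75% attendance record in the experimental group include receiving a Fitbit Inspire HR for the study". The control-arm rule follows later in the same paragraph: "Control group participants will also each receive Fitbit Inspire HR upon completion of all pre- and post-survey measures as an incentive". The control rule has no attendance condition, and the experimental rule as written has no survey condition.

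The measures table under Sources of Materials has a row headed "Collection of secondary data, including attendance and academic data", with this timing: "Attendance data: Collected 8 weeks prior to study and during 8 weeks of intervention for comparison". Absenteeism is also part of the reason for the January to March window, since "this timeframe has shown a historical spike in inappropriate student behaviors and absenteeism". Aim 1 states that "the study will compare results between the experimental group and a new 20-participant control group".

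The SAP does not name attendance. It treats secondary academic performance outcomes descriptively, as a proxy for well-being, and the section on salivary cortisol ends by bringing secondary academic and behavioural data together with the other results. The Physical Health Measures section has participants wearing the Fitbit from one week before the intervention starts.

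**The concern.** The reward in one arm acts on something the study measures, during the weeks in which it is measured. The other arm's reward acts on something else. If yoga students attend more, the reader cannot tell whether yoga or the device brought them in.

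Absenteeism helped to set the study window, and results feed a decision about a year 3 expansion. A gain bought by a device could be read there as a benefit of yoga.

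A second, weaker route runs through the surveys. Only control students are described as earning the device by completing them, so T1 self-report completion might differ by arm. The SAP gives no missing-data method.

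**Working it through.** The plan states no figure for this point, so there is nothing to reproduce. The check is a comparison of the rules, followed by an illustration of size.

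**1. The two arms side by side**

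| | Experimental (2 classes, 35 students) | Control (1 class, 20 students) |
|---|---|---|
| Device | Fitbit Inspire HR | Fitbit Inspire HR |
| Earned by | at least 75% attendance | completing pre- and post-surveys |
| Attendance measured | 8 weeks before, 8 weeks during | the table row makes no distinction by arm |

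**2. Does the pre/post comparison remove the reward effect?** Let τ be the yoga effect on attendance and ρ the effect of the attendance reward. Both are absent in the 8 weeks before the study. Leaving class differences aside:

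- change in experimental arm = common time trend + τ + ρ
- change in control arm = common time trend
- difference = τ + ρ

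The trend cancels and ρ does not. (Control students must be present to complete surveys, but continuing attendance is not rewarded.)

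**3. Does the SAP's model remove it?** The covariates are grade, gender, prior yoga exposure at the school and time point, with condition and condition by time added for the intervention effect. The attendance reward applies to every experimental student and no control student, so an indicator for it would be identical to condition. The two are fully aliased, and no adjustment can separate them.

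**4. The threshold, if sessions are what is rewarded.** Sessions are described thus: "Twice weekly 45-minute sessions during the 8-week intervention period will occur within two physical education classes". That gives 2 × 8 = 16 sessions. Then 0.75 × 16 = 12, so a student may miss 16 − 12 = 4.

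**5. Illustration of size, with τ = 0.** These assumptions are not in the documents: sessions attended, X, follow a beta-binomial distribution over 16 sessions with beta precision 8, and students who would fall below 12 close a fraction q of their gap because of the reward.

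Lift in percentage points = 100 × q × E[max(0, 12 − X)] / 16

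| Assumed baseline attendance | P(X < 12) | Lift in sessions, q = 1 | Points, q = 0.25 | Points, q = 0.5 | Points, q = 1 |
|---|---|---|---|---|---|
| 75% | 0.382 | 1.13 | 1.8 | 3.5 | 7.1 |
| 80% | 0.273 | 0.74 | 1.2 | 2.3 | 4.6 |
| 85% | 0.174 | 0.43 | 0.7 | 1.3 | 2.7 |
| 90% | 0.092 | 0.21 | 0.3 | 0.7 | 1.3 |

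**6. From sessions to school days.** The lifts above are in session attendance. If the measured outcome is school attendance, and the reward acts only on yoga days in a five-day week (assumption), the shift is 2/5 = 40% of the lift:

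- 90% baseline: 0.4 × 0.3 = 0.12 to 0.4 × 1.3 = 0.52 points, or about 0.1 to 0.5
- 75% baseline: 0.4 × 1.8 = 0.72 to 0.4 × 7.1 = 2.84 points, or about 0.7 to 2.8

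If school attendance itself is what is rewarded, the reward acts on the outcome directly and this dilution does not apply.

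**The case against.** The strongest reply is that little rests on attendance. It is secondary data, no hypothesis or test is specified for it, and the between-arm contrast has to be inferred from the general statement in Aim 1. Effectiveness is to be judged on the depression and anxiety surveys, the wearable and cortisol. This stands, and it limits the point to how one measure is interpreted. It does not remove the point, because a descriptive contrast carries the same reward effect as a tested one.

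A reader might infer that control students get no incentive. The documents say otherwise: both arms can earn the same device, and only the condition differs. Because participants wear the Fitbit before any attendance could be earned, it may be keeping the device that is conditional. The force of the reward is therefore unclear, but the attendance condition still applies to one arm only.

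The effect on school attendance may also be diluted. Sessions touch two days a week, and Aim 2 places one remote session outside the school day, where attending adds nothing to school attendance. That bears on size, not on separability.

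On the surveys, the reply largely succeeds. Teacher and parent survey incentives are not arm-specific, and the list of experimental-arm incentives may not be exhaustive. A reader might infer that T1 missingness will be unequal. The documents do not show that, so it remains a possibility affecting student self-reports.

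Finally, an attendance reward has a legitimate purpose in a pilot that wants students to receive the intervention. That argues for a rule that keeps this lever in both arms.

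**Conclusion.** The point holds as a limit on interpretation. A between-arm attendance difference would estimate yoga plus an attendance reward, and nothing planned can separate the two. That conclusion follows from the two earning rules and the measurement window, and needs no numerical assumption.

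If the reward changes attendance at all, the direction favours yoga. The size cannot be given. The ranges in the working rest on an assumed attendance distribution, response to the reward and baseline, and serve only to show that the effect could run from negligible to several points.

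Three stronger readings go too far:

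- **That the attendance result is certain to be biased.** This would require the reward to alter behaviour materially, which the documents cannot show.
- **That the anxiety and depression results are compromised.** They are touched only through the possible difference in T1 completion.
- **That equal incentives would make an attendance difference attributable to yoga.** With one control class, arm stays confounded with class, so equalising the rule removes one source of bias and leaves that one.

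**What to change.** Use one earning rule for every student in the three PE classes. Either version works:

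- **Attendance plus surveys for all.** Require at least 75% PE-class attendance and completion of the T0 and T1 surveys in both arms. This keeps the adherence lever. Count only PE-class meetings that both arms have, so that the session taken from home under Aim 2 does not enter the rule. The contrast then estimates the yoga effect with an attendance reward in place for all.
- **Survey completion alone for all.** This is simpler and also equalises the incentive to respond at T1. The small downside is losing the attendance lever.

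In the same edit, state whether the attendance record means yoga or PE sessions or school days, and whether the measured outcome is PE or school-wide attendance. Reconcile the rule with the Physical Health Measures section by saying whether wearing the device or keeping it is conditional.

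If the rule cannot be changed, say in the SAP that the attendance contrast will be reported descriptively as the effect of yoga plus the attendance incentive, and not of yoga.

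In every case, state that one control class leaves arm confounded with class.

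The cost is wording in the protocol and in the assent and consent forms. Devices are already planned for both arms.

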### **Statistical Analysis Plan**

Gym class clusters of individuals will be randomly allocated to intervention groups. This approach is necessary because randomization at the individual level is impractical and we strive to avoid contamination between treatment groups. The responses from individuals within a cluster are likely to be more similar than those from different clusters because individuals within a will share a common yoga class experience. This lack of independence introduces complexity to the design and analysis. The degree of similarity, or clustering, will be quantified and reported using the intraclass correlation coefficient (ICC). When the ICC is low, individual observations contribute nearly equally to the analysis. (38). For all participants, baseline surveys (see table above) will be conducted prior to exposure to Yoga (T0). Follow-up surveys will be collected at 8 weeks (T1). Analyses will be conducted using R Version 3.6. Baseline differences between intervention and control group will be examined using independent *t* test or  $\chi^2$  test. All data will be analyzed according to treatment assignment. Two strategies will estimate treatment effects: 1) Cluster level analysis using summary measures; and 2) Individual level analysis adjusted for clustering to appropriately account for the nested structure of data and cluster randomization in

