estimating. For the first, we will measure mean outcomes by cluster followed by parametric t-tests or non-parametric tests, depending on the distributions of the outcome measures. To account for the variability between gym classes and nested structure of the data, multilevel mixed-effects models will be used for each continuous outcome, with time (T0 & T1) as level 1, students as level 2, and class as level 3. To adjust for baseline pre-treatment values, explanatory variables for each outcome will include grade, gender, prior exposure to yoga at the high school, and survey time point (model 1). To assess the intervention's effect on outcomes, we will use condition (intervention or control) and the interaction between condition and time as predictors (model 2). Effect sizes (ESs) will be calculated as (estimated intervention effect)/ $\sqrt{\text{variance at student level}}$ . Interpretation of ES will determine the gains of the intervention versus control group. To calculate power for this cluster randomized trials that compares two means, we used the "clusterPower" package in R (24). Accounting for clustered design effects, 55 participants with variation in cluster sizes, an assumed low intraclass correlation of 0.001, and within-cluster variation of 5 units, this would provide at least 65% power to detect clinically meaningful effects between the treatment and control arm using two-sided tests at  $\alpha=0.05$ . To maximize test power and precision of estimation considering the few clusters in this study, we will also use wild cluster bootstrap-t procedure to correct our standard errors (9, 47).

A proxy for improved well-being, secondary academic performance outcomes, will also be analyzed descriptively pre- (during week 1) and post-intervention (at the end of week 8) (see table above).

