### ***Physical Health Measures.***

Participants enrolled will have their resting heart rate and restorative sleep data tracked and assessed using their Fitbit Inspire HR wristbands. They will be instructed to begin wearing their Fitbit for 1 week prior to starting the intervention to establish baseline data for sleep cycles and resting heart rates; this will also allow the PI to monitor daily data collection to ensure all devices are recording properly and address malfunctions and/or user error prior to the intervention. Once the intervention has begun, the PI will asynchronously and wirelessly connect to their Fitbit data using the Fitabase cloud-based data management platform once weekly to track any changes in duration and quality of restorative sleep and changes in resting heart rate.

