***Control Group.***

Volunteers will participate in a separate physical education class for 8 weeks and will undergo testing as described above, with an opportunity to participate in yoga after T1.

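### Controls are to receive the Fitbit only after the post-survey, which conflicts with the tracking schedule; followed as worded, heart rate and sleep have no control baseline

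*Combined protocol and SAP*

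**What the plan says.** All references are to the combined protocol and SAP.

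- **Study Protocol, incentives, control arm:** "Control group participants will also each receive Fitbit Inspire HR upon completion of all pre- and post-survey measures as an incentive". For the yoga arm, the same paragraph describes the device as serving to track physical health data during the study, to be kept afterwards, and ties it to attendance of at least 75%. It states no tracking purpose for controls.
- **Statistical Analysis Plan, timing:** follow-up surveys are at 8 weeks (T1).
- **Physical Health Measures:** "Participants enrolled will have their resting heart rate and restorative sleep data tracked and assessed using their Fitbit Inspire HR wristbands", and "They will be instructed to begin wearing their Fitbit for 1 week prior to starting the intervention to establish baseline data". Neither sentence names or excludes an arm.
- **Sources of Materials, table:** tracker data are due one week before the intervention, at week 4 and at the end of week 8, again with no limit to one arm.
- **Control Group:** controls "will undergo testing as described above, with an opportunity to participate in yoga after T1". This section follows both the Fitbit and the cortisol sections.
- **Aim 1:** the tracker, with resting heart rate and sleep patterns, is listed among the means of assessing effectiveness, and results are to be compared with a 20-student control group.
- **Statistical Analysis Plan, model:** "multilevel mixed-effects models will be used for each continuous outcome". Model 2 adds condition and the condition-by-time interaction.

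**The concern.** A control student who receives a device only after finishing the post-survey cannot have worn it in the baseline week or at week 4. That contradicts the sections that have enrolled students tracked from before the intervention and controls tested in the same way. The contradiction with the Aim 1 comparison and the Sources of Materials timetable is by implication only, since neither says who wears a device when.

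At stake is whether two of the effectiveness measures have a control comparison at all. Without control baselines they become an uncontrolled before/after series in the yoga classes. The study window was chosen because January to March has historically shown more behavior problems and absenteeism, so a seasonal change in students is plausible, and a one-arm series cannot separate it from an effect of yoga. Other wording faults can be corrected later. A baseline week that was not recorded cannot be.

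**Working it through.** The plan states no figure on this point, so there is none to reproduce. The check is a comparison of timelines, followed by a count of what each reading leaves to analyze.

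**Inputs.** 35 yoga students and 20 controls (Study Protocol); 3 gym classes, of which 2 yoga and 1 control (Study Protocol); 3 scheduled tracker time points (Sources of Materials); post-survey at 8 weeks (Statistical Analysis Plan). Weekly downloads (Physical Health Measures) would give more readings than the 3 counted here.

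**Step 1: control readings under each reading of the text.**

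| Time point | Hand-out wording followed | Tracking text followed |
|---|---|---|
| 1 week before | 0 of 20 | 20 of 20 |
| Week 4 | 0 of 20 | 20 of 20 |
| End of week 8 | 20 of 20 at best; 0 of 20 if handed out after the reading | 20 of 20 |

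**Step 2: share of scheduled readings lost, per measure.**

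- Scheduled: (35 + 20) × 3 = 165.
- Baseline and week 4 lost in controls: 20 × 2 = 40; 40/165 = 24%.
- Week 8 lost as well: 20 × 3 = 60; 60/165 = 36%.
- Tracking text followed: 0 of 165 lost.

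**Step 3: change from baseline.** Available for 0 of 20 controls and at most 35 of 55 students (35/55 = 64%), from 2 of the 3 classes, both yoga.

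**Step 4: can the planned effect be estimated?** Let T = 0 at T0 and 1 at T1, and C = 1 for yoga and 0 for control. The fixed part of model 2, leaving covariates aside, is

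E(Y) = b0 + b1·T + b2·C + b3·T·C.

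The intervention effect is

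b3 = (yoga T1 − yoga T0) − (control T1 − control T0),

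which needs all four cell means. The design has 4 columns. Its rank equals the number of occupied cells:

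| Cells observed | Rows | Rank |
|---|---|---|
| All four | 55 × 2 = 110 | 4 |
| Control T0 empty | 110 − 20 = 90 | 3 |
| Control T0 and T1 empty | 110 − 40 = 70 | 2 |

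With control T0 empty, the control change does not exist, so b3 is not estimable. Grade, gender and prior yoga exposure do not supply the missing cell. At best a T1-only contrast with the one control class remains, with no baseline adjustment. Steps 1 and 2 use the three tracker time points. Step 4 uses T0 and T1 because those are the time levels that the model names.

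**The case against.** The strongest reply is that the sentence describes what controls earn, not when they first wear a device. It stands in an incentive paragraph, and the yoga-arm sentence there is just as loose: a 75% attendance record cannot be known one week before the first session, so taken literally the yoga arm would have no baseline device either. The operational text (Physical Health Measures, the timetable and Control Group) all points to tracking everyone. On that reading controls wear a device throughout and own it at the end, and nothing is lost.

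Part of this stands. The reading is possible, and the yoga-arm sentence does have a timing problem of its own. Every loss counted above is therefore conditional. But the two arms are not worded alike: only the yoga device is said to be for tracking during the study. No text states a loan to controls. The Salivary Cortisol Assays section names both groups, whereas Physical Health Measures names neither. Staff handing out devices could reasonably follow the incentive sentence as written. Consent and assent pages, which are not in the text reviewed, may settle the timing, but the protocol should not leave it open.

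It is also fair to say that this is a feasibility study, that heart rate and sleep are two of many measures, and that none is named primary. That limits the weight of the point without answering it, because Aim 1 lists these measures under effectiveness. Declaring tracking to be yoga-arm only would also remove the contradiction, but it would give up the control comparison for these measures.

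**Conclusion.** The concern holds, and the plan should be corrected before devices are handed out. The texts on when controls have the Fitbit conflict as written.

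If the hand-out wording is followed, no control has a baseline, 24% to 36% of scheduled readings per measure are absent, all of them among controls, and the condition-by-time effect is not estimable for resting heart rate or sleep. This assumes that yoga students wear devices from the baseline week, as the tracking purpose stated for that arm implies, and that controls have no device from another source. If the tracking text governs, 0 of 165 readings are lost and the fault is one of wording only. The documents do not say which reading is intended.

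The single control class is a separate limitation. Complete tracker data would restore the planned comparison but would not separate arm from class.

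**What to change.** 1. In Study Protocol, state that students in both arms are issued the Fitbit one week before week 1 and wear it through week 8. Let the existing conditions (75% attendance in the yoga arm, survey completion in the control arm) decide only who keeps it. This also removes the yoga arm's timing problem.
2. In Physical Health Measures, state that both groups are tracked and compared on resting heart rate and sleep, in the way that Salivary Cortisol Assays names both groups for sample collection.
3. Align the assent and consent text if it says otherwise.

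**Cost.** Mostly wording and an earlier hand-out date for controls. The plan already provides for up to 35 + 20 = 55 devices, so no more are needed. That figure is a maximum, since both awards are conditional, and issuing devices beforehand requires all 55. The other costs are weekly downloads for 20 more students and some risk of devices being lost or not returned. Both incentives are kept.

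### Attendance is compared before and during the study, but only the yoga arm, and only during the study, has a reward tied to attendance

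*Combined protocol and SAP*

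**What the plan says.** - **Outcome.** The secondary-data row of the measures table (Sources of Materials) reads: "Attendance data: Collected 8 weeks prior to study and during 8 weeks of intervention for comparison".
- **Sessions.** The Study Protocol section places yoga inside that second window: "Twice weekly 45-minute sessions during the 8-week intervention period will occur within two physical education classes".
- **Reward, yoga arm.** The same section states: "Student incentives for at least a 75% attendance record in the experimental group include receiving a Fitbit Inspire HR for the study".
- **Reward, control arm.** "Control group participants will also each receive Fitbit Inspire HR upon completion of all pre- and post-survey measures as an incentive". No attendance condition is stated for controls.
- **Analysis.** The Statistical Analysis Plan says: "A proxy for improved well-being, secondary academic performance outcomes, will also be analyzed descriptively", and points back to the measures table.
- **Remote session.** Aim 2 describes two remote sessions. One is in the PE period; "another will be held outside of the regular school day with participants attending synchronously from home". The text does not say whether this one belongs to the twice-weekly series or counts toward the 75%.

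Nothing in the documents removes session days or periods from the attendance outcome, or adjusts for the reward. The documents also do not define the unit of attendance (whole day, all classes or PE only), or say whether the 75% means yoga sessions or school attendance in general.

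**The concern.** Presence at a yoga session during school is both adherence to the intervention and, unless it is excluded, part of the attendance outcome. The yoga arm has a material reason to be present that did not exist in the 8 weeks before the study and does not exist in the control class. A gain in attendance could then be reported as a result of yoga when some of it was a response to the incentive.

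This would remain with equal numbers of school days in both windows, complete data and a concurrent control class. It is therefore separate from any question of seasonality or missing data. It matters because absenteeism is one of the two problems for which the district chose the January to March window, so an attendance gain is likely to be noticed even if it is only described.

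**Working it through.** **1. Where the reward acts.** Let S be the seasonal change in absence, Y the effect of yoga and R the effect of the reward.

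| | 8 weeks before | 8 weeks during | Change |
|---|---|---|---|
| Yoga (35 students) | base | base + S + Y + R | S + Y + R |
| Control (20 students) | base | base + S | S |

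The before/during change in the yoga arm is S + Y + R. The between-arm difference in change is Y + R. R stays in both, because it sits in one cell only. The protocol expects S to be a rise in absences, so R may show as a smaller rise than in controls rather than as a fall.

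**2. Inputs.** From the documents: 2 sessions × 8 weeks = 16 sessions; 75% of 16 = 12, so up to 4 may be missed. Assumed: 5 school days × 8 weeks = 40 days, no holidays, and no effect of yoga (Y = 0). The plan states no attendance figure, so there is none to reproduce.

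**3. Whole-day attendance, proportional response.** If the reward cuts absence on session days by a fraction f, the relative fall in total absences is (16/40) × f = 0.40f.

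| f | Fall in total absences | 4.0 days absent (assumed 10% rate) becomes |
|---|---|---|
| 10% | 4% | 3.84 |
| 25% | 10% | 3.6 |
| 50% | 20% | 3.2 |

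If one of the 16 is the out-of-school remote session, the share is 15/40 = 37.5%.

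**4. Whole-day attendance, response only at the threshold.** Suppose only students who would miss more than 4 sessions respond, and each attends just enough to reach 12. With X the number of sessions missed and m the mean absence rate, the relative fall is E[max(X − 4, 0)] / (40m). X is beta-binomial (16 sessions, mean m); higher precision means less spread between students.

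| Mean absence | Precision | Fall in total absences |
|---|---|---|
| 5% | 20 | 1.0% |
| 10% | no spread | 0.5% |
| 10% | 20 | 2.4% |
| 10% | 10 | 4.3% |
| 10% | 5 | 7.6% |
| 15% | 5 | 9.4% |
| 20% | 5 | 11.3% |
| 15% | 3 | 12.4% |
| 20% | 3 | 13.9% |

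The result depends mainly on the assumed mean and spread. The 24 non-session days (40 − 16) are unchanged in every row.

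**5. Attendance by class period.** With 6 to 8 periods a day (assumed), the sessions are 16/240 = 6.7% to 16/320 = 5.0% of the record. At f = 25% the fall is about 1.7% to 1.25%, without spill-over. If only PE periods are counted, the share depends on how often PE meets, which is not stated.

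**6. If the 75% means school attendance in general.** Every day is rewarded and the fall is f itself.

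**The case against.** **Little in the plan rests on attendance.** Aim 1 names the measures of effectiveness as depression and anxiety surveys, the tracker and cortisol; attendance is not among them. This stands, and it makes the point a cheap improvement rather than a threat to the trial.

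**A reader might infer that the plan treats attendance as a proxy for well-being.** The documents do not establish this. The proxy sentence concerns academic performance outcomes taken in week 1 and at the end of week 8. That timing fits the standardized test scores better than totals over two 8-week windows, and the table names attendance and academic data separately. The pointer to the table makes the wider reading possible, but no more than that.

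**A reader might also take 40% as the share of the outcome that is rewarded.** That holds only for whole-day counting, over an assumed 40 days with all 16 sessions on school days.

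**Most students may reach the threshold anyway.** With independent absences and no reward effect, the chance of attending at least 12 of 16 is 98% at a 10% absence rate, 80% at 20% and 63% at 25%. So the proportional model in step 3 may overstate the response, and the upper rows of step 4 need wide spread and full response by every student over the limit. What remains is that students with high absence are the ones on whom both the incentive and an absenteeism outcome turn.

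**The incentive's timing is unclear.** Under Physical Health Measures, participants wear the device from one week before the intervention. The 75% rule may govern keeping it rather than receiving it. That could change how strongly the rule acts, but an attendance condition on the yoga arm alone remains either way.

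**Conclusion.** The point holds as a possible bias in one secondary measure, in favour of yoga. The attendance reward exists in one arm and one period, and neither planned comparison separates it from an effect of yoga.

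Its size is unknown. With no yoga effect and whole-day counting, the illustrations run from 4% to 20% fewer absences if session-day absence falls by 10% to 50%, and from about 0.5% to 14% across the cases tried if only students over the 4-absence limit respond. Counting by class period brings the 25% case down to between 1% and 2%. A 75% rule on all school attendance would expose every day. All of these rest on assumed absence rates, response, calendar and unit of attendance.

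The documents do not support the stronger inference that an observed attendance gain would be only the product of the reward. Nor does this point reach the depression, anxiety, tracker or cortisol outcomes.

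**What to change.** - **Measures table and Statistical Analysis Plan.** Define the attendance outcome as absences per enrolled school day on non-yoga days or, if attendance is recorded by period, absences in non-PE periods. Use the same weekdays or periods before and during, in all three classes, as far as the school's records allow.
- **Adherence.** Report presence at the yoga sessions separately as adherence. Show total attendance alongside the restricted measure, labelled as affected by the incentive, so that readers can see how much of any change falls on rewarded days.
- **Study Protocol, incentives.** State what the 75% refers to, and whether the out-of-school remote session counts toward it. Reconcile this with Physical Health Measures, where the device is worn from one week before the intervention.
- **If the 75% means all school attendance,** do not present attendance as evidence of a benefit of yoga.

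**Cost.** About one sentence in each place, and no change to the incentive itself. It needs attendance records by date or period, which the documents do not confirm, and matching weekdays needs fixed yoga days, which are not stated. Excluding whole days loses up to about 40% of days from the measure; excluding PE periods loses less. Spill-over of the reward to other days or periods is not removed and should be named as a limitation.
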